**Pharmacokinetic Parameters Following the Last Dose (Day 29):**

*Note: The following parameters will be calculated using the data through 24 hours for the once daily dosing regimens or through the EOS/ET sample on Day 57 (ie, 28 days post Day 29 dose) for the monthly dosing regimens, where possible.*

$C_{max}$ :	Maximum concentration during the dosing interval (24 hours for once daily and 28 days for monthly), observed by inspection of individual study participant concentration-time profiles.
$C_{max,0-24h}$ :	Maximum concentration over a 24-hour interval, observed by inspection of individual study participant concentration-time profiles. Presented for the monthly dosing regimens only. (For the daily dosing regimens, $C_{max}$ will be equivalent to $C_{max,0-24h}$ .)
$T_{max}$ :	Time of maximum concentration during the dosing interval (24 hours for once daily and 28 days for monthly), obtained directly from the observed concentration-time data.
$T_{max,0-24h}$ :	Time of maximum concentration over a 24-hour interval, obtained directly from the observed concentration-time data. Presented for the monthly dosing regimens only. (For the daily dosing regimens, $T_{max}$ will be equivalent to $T_{max,0-24h}$ .)
$AUC_{0-t}$ :	AUC from time 0 to the last measurable time point, calculated by linear-log trapezoidal summation.
$AUC_{\tau}$ :	AUC during the dosing interval ( $\tau$ ), where $\tau = 24$ hours for the daily dosing regimens and $\tau = 28$ days for the monthly dosing regimens.
$AUC_{0-t'}$ :	AUC from time 0 to a fixed time point $t$ , calculated by linear-log trapezoidal summation. This will include the $AUC_{0-24h}$ for the monthly dosing regimens (equivalent to $AUC_{\tau}$ for the daily dosing regimens).
$C_{avg}$ :	Average concentration over a dosing interval after multiple doses, calculated as $AUC_{\tau}/\tau$ . For the monthly dosing regimens, average exposure over a 24-hour interval ( $C_{avg,24h} = AUC_{0-24h}/24$ hours) and/or over the entire dosing interval ( $C_{avg,28d} = AUC_{0-28d}/28$ days).
$RA,C_{max}$	Accumulation ratio based on $C_{max}$ , calculated as $(C_{max}, \text{Day 29})/(C_{max}, \text{Day 1})$ .
$RA,AUC$	Accumulation ratio based on AUC. For once daily dosing regimens, calculated as $(AUC_{\tau}, \text{Day 29})/(AUC_{0-24h}, \text{Day 1})$ . For monthly dosing regimens, AUCs from 0 to 24 hours or 28 days may be used, as deemed appropriate.
LF	Linearity factor, calculated as $(AUC_{\tau}, \text{Day 29})/(AUC_{0-\infty}, \text{Day 1})$ (paricalcitol only).

$\lambda_z$ :	Terminal elimination rate constant (if estimable), determined by linear regression of the terminal points of the log-linear concentration-time profile (paricalcitol only).  Calculation of $\lambda_z$ requires a minimum of 3 data points after (and not including) $C_{max}$ . The $R^2$ -adj for the linear regression must be at least 0.80.
$t_{1/2}$ :	Terminal elimination half-life (if estimable), determined as $[\ln(2)/\lambda_z]$ (paricalcitol only).
$CL_{ss}/F$ :	Apparent clearance after multiple extravascular administrations, calculated as Dose/ $AUC_{tau}$ (calculated for paricalcitol and for BL-adjusted calcifediol following the calcifediol treatments only, where possible).

In addition to the above parameters, measures of exposure over the entire 56-day study period will be determined for calcifediol (for the monthly dosing regimens only), according to the following calculations:

- $AUC_{0-56d}$ : AUC over the entire study period (56 days), calculated as  $(AUC_{0-28d}, \text{Day 1}) + (AUC_{tau}, \text{Day 29})$ ;
- $C_{avg,56d}$ : Average concentration over the entire study period (56 days), calculated as  $AUC_{0-56d}/56$  days.

All subjects in the PK population will be included in the descriptive statistics for the PK parameters. No value for  $\lambda_z$ ,  $AUC_{0-inf}$ ,  $AUC_{ext}$ ,  $CL/F$ ,  $V_d/F$ ,  $T_{ss}$ , or  $t_{1/2}$  will be reported for cases that do not exhibit a terminal log-linear phase in the concentration-time profile. No PK parameters will be calculated for subjects with insufficient data following BLQ imputation, see Section 5.5 (eg, fewer than 3 quantifiable postdose concentrations for AUC,  $\lambda_z$ , and associated parameters;  $C_{max}$  and  $T_{max}$  parameters may be presented for subjects with fewer quantifiable concentrations, if deemed appropriate).

Descriptive statistics of PK parameters for calcifediol and paracalcitol will be provided for the PK population by visit and treatment and will include number of subjects, mean, SD, CV%, median, minimum, maximum, geometric mean and geometric CV%.

Subgroups will also be presented for subjects who received the full dose of study drug versus those who received dose adjustments (ie, summaries provided for paricalcitol 1 mcg and 2 mcg on Day 29, where categories will be determined once the study is complete).

All calculated PK parameters will be presented in a data listing.

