1.9 Previous Clinical Experience with CTAP101

CTAP101 Capsules (30 mcg) have been approved as Rayaldee® by the US Food and Drug Administration (FDA) for the treatment of SHPT in adults with stage 3 or 4 CKD and VDI,

defined as serum total 25-hydroxyvitamin D levels less than 30 ng/mL. The clinical studies which supported FDA approval are described below.

There have been three previous single-dose phase 1 studies with CTAP101 Capsules ([CTAP101-CL-1005](#), [CTAP101-CL-1011](#) and [CTAP101-CL-1016](#)), two phase 2 studies, of which one was a single-dose study ([CTAP101-CL-2004](#)) and one was a repeat-dose study ([CTAP101-CL-2008](#)), and three phase 3 studies ([CTAP101-CL-3001](#), [CTAP101-CL-3002](#) and [CTAP101-CL-3003](#)). Studies CTAP101-CL-1011, CTAP-CL-1016 and CTAP101-CL-2008 were conducted with the current formulation of CTAP101 Capsules (30 mcg per capsule). Two of the phase 3 studies (CTAP101-CL-3001 and CTAP101-CL-3002) were identical double-blind, placebo-controlled pivotal trials and the third (CTAP101-CL-3003) was a follow-on open-label extension trial.

The single-dose studies confirmed the ER characteristics of the investigational drug product and that the current formulation has a BA of approximately 25% when administered in the fasting state. Administration of a single pharmacologic dose of CTAP101 Capsules following a high-fat, high calorie meal resulted in a significantly higher exposure of calcifediol compared to when administered in a fasted state. An approximate 5-fold increase in maximum serum concentration (C_{max}) and a 3.5-fold increase in area under the concentration curve (AUC) was observed in the fed group compared to the fasted group (CTAP101-CL-1016).

In CTAP101-CL-2008, a double-blind, placebo-controlled, randomized repeat-dose study, daily administration of CTAP101 Capsules increased serum total 25-hydroxyvitamin D levels to ≥ 30 ng/mL in nearly all subjects and decreased mean plasma iPTH from pre-treatment baseline (BL) and compared to placebo during 6 weeks of treatment. The mean % decrease in iPTH from BL in the per-protocol (PP) population was related to the administered dose: -20.9, -32.8, and -39.3 for the 30, 60 and 90 mcg groups, respectively.

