A phase 2b dose ranging study in which CTAP101 Capsules were administered at daily doses of 30, 60 and 90 mcg (or 210, 420 and 630 mcg/week) for six weeks showed that mean plasma iPTH decreased from pre-treatment BL in a dose-proportional manner by 20.9, 32.8 and 39.3%, respectively, and that serum total 25-hydroxyvitamin D rose to levels \geq 30 ng/mL in almost all subjects ([CTAP101-CL-2008](#)). The daily doses of 30 and 60 mcg increased serum 25-hydroxyvitamin D to a mean levels of 37 and 67 ng/mL, respectively, well within the range of 30 to 100 ng/mL. The daily dose of 90 mcg raised mean serum 25-hydroxyvitamin D at EOT to 85 ng/mL causing levels to exceed 100 ng/mL in a substantial proportion of subjects. This dose was considered too high for further evaluation in the phase 3 studies. AE rates were comparable across the treatment groups, indicating that therapy with CTAP101 Capsules had no adverse effect on mean serum calcium or phosphorus or on any other monitored parameters during the 6-week treatment period. PK analyses determined that the terminal elimination half-life $t_{1/2}$ after repeat dosing was approximately 30 days but that steady state was not yet achieved after 6 weeks of treatment. Steady state was determined in phase 3 studies to be attained after 12 weeks of treatment ([CTAP101-CL-3001](#) and [CTAP101-CL-3002](#)).

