5.5.2 Diet Restrictions

There are no study specific dietary restrictions. Subjects should follow their dietary plan if one has been prescribed. Changes in prescribed dietary phosphorus or calcium therapy are discouraged and any changes during the study should be captured in the electronic case report form (eCRF).

Subjects will maintain a dietary intake during the study of approximately 1,000-1,500 mg per day of elemental calcium per dietary counseling and, as necessary, administration of a daily calcium supplement. Subjects will complete a dietary questionnaire on Visit 1 and receive counseling from a dietitian on their dietary calcium intakes, if needed.

Subjects will report to the phase 1 unit on the mornings of Day 1 and Day 29 after an overnight fast. They will receive standardized meals while housed in the phase 1 unit. These meals will contain 400 mg of elemental calcium and will be administered at approximately 2, 6, and 10 hours post-dose.

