5.2 Pharmacokinetic properties

Absorption

Calcifediol or 25-hydroxycholecalciferol, such as vitamin D analogues, is absorbed in the intestine if the absorption of fats is normal, through the chylomicrons, principally in the middle sections of the small intestine; approximately 75–80% is absorbed this way.

Distribution

Calcifediol is the main circulating form of vitamin D. The serum concentrations of 25(OH)-cholecalciferol reflect the organism's vitamin D reserves which are usually between 25 and 40 ng/mL (62.5 to 100 nmol/L) in healthy individuals. Following the oral administration of calcifediol, the time in which the maximum serum concentration is reached is approximately 4 hours. Its half-life is around 18 to 21 days and its storage in the adipose tissue is less significant than that of vitamin D, due to its lower liposolubility; calcifediol is stored in the adipose and muscle tissue for extended periods of time. The pharmaceutical form of soft capsules offers a 22% higher bioavailability than the pharmaceutical form of an oral solution in vials. This difference is not considered clinically significant given that the dose must be determined on an individual basis depending on the serum levels of 25-OH-cholecalciferol and calcium, and these levels must be controlled during the treatment.

Metabolism or Biotransformation

Elimination

Calcifediol is principally excreted in the bile.

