$\lambda_z$ :	Terminal elimination rate constant (if estimable), determined by linear regression of the terminal points of the log-linear concentration-time profile (paricalcitol only).  Calculation of $\lambda_z$ requires a minimum of 3 data points after (and not including) $C_{\text{max}}$ . The adjusted coefficient of determination ( $R^2\text{-adj}$ ) for the linear regression must be at least 0.80.
$t_{1/2}$ :	Terminal elimination half-life (if estimable), determined as $[\ln(2)/\lambda_z]$ (paricalcitol only).
$CL/F$ :	Apparent clearance after extravascular administration, calculated as $\text{Dose}/AUC_{0-\infty}$ (paricalcitol only).
$V_d/F$ :	Apparent volume of distribution after extravascular administration, calculated as $\text{Dose}/(\lambda_z \times AUC_{0-\infty})$ (paricalcitol only).
$T_{\text{ss}}$ :	Predicted time to steady state, calculated as $(t_{1/2} \times 5)$ (paricalcitol only).

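### SAP 7.2: Day 29 Dose/AUCtau for CTAP101 is not a clearance because steady state is not reached, and the RA and LF ratios ignore dose changes between Day 1 and Day 29

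*SAP*

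**What the plan says.** SAP 7.2 defines CLss/F after the Day 29 dose as Dose/AUCtau, "calculated for paricalcitol and for BL-adjusted calcifediol following the calcifediol treatments only, where possible". For the daily regimens tau is 24 hours, so for CTAP101 this is the interval of the 29th daily dose. No steady-state condition is attached.

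Protocol 3.2 says of CTAP101 that the terminal half-life "after repeat dosing was approximately 30 days", that "steady state was not yet achieved after 6 weeks of treatment", and: "Steady state was determined in phase 3 studies to be attained after 12 weeks of treatment".

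The same SAP section defines RA,Cmax and RA,AUC as the Day 29 value over the Day 1 value, and LF (paricalcitol only) as Day 29 AUCtau over Day 1 AUC0-inf. None has a dose term. Yet the dose can change in between. Paricalcitol may double from 1 to 2 mcg after four weeks (Protocol 5.2; the Synopsis places this at Day 29), and CTAP101 may be halved or suspended at any time (Protocol 5.3, SAP 3.3).

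SAP 7.1 and 7.2 plan subgroup summaries by full versus adjusted dose. They name paricalcitol 1 mcg and 2 mcg on Day 29 and leave further categories until the study is complete. The main summaries include the whole PK population.

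**The concern.** Dose/AUCtau equals apparent clearance only when drug eliminated over the interval balances the dose given, that is, at steady state. By the sponsor's own account CTAP101 is still accumulating at week 4, so a reader who takes the CLss/F row as a clearance is misled.

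A Day 29/Day 1 ratio measures accumulation or linearity only if the dose is constant. After up-titration, LF exceeds 1 under perfectly linear kinetics and so signals a non-linearity that does not exist. After a CTAP101 reduction, accumulation looks smaller than it is. These parameters are listed PK endpoints in SAP 2.2.2, and Protocol 3.2 makes repeated-dose calcifediol PK a principal aim.

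**Working it through.** The plan states no value for CLss/F, RA or LF, so there is no figure to reproduce. The check uses one-compartment linear superposition with a constant endogenous baseline and no absorption lag.

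**CTAP101, equal bioavailability.** The fraction of steady-state AUCtau reached with daily dose *k* is 1 − 2^(−*k*/t½), with *k* = 29. Dose/AUCtau is too high by the inverse of this fraction. Two half-lives are used because the two statements in Protocol 3.2 do not agree exactly in this model:

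- 30 days, as stated: 1 − 2^(−29/30) = 0.488, so 1/0.488 = 2.05. This half-life implies 62% of steady state at 6 weeks and 86% at 12 weeks.
- 84/5 = 16.8 days, from reading 12 weeks through the SAP rule "Predicted time to steady state, calculated as" five half-lives (stated there for paricalcitol only): 1 − 2^(−29/16.8) = 0.698, so 1.43. This implies 82% and 97%.

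**CTAP101, unequal bioavailability.** Subjects are dosed in the unit "on the mornings of Day 1 and Day 29 after an overnight fast", and at bedtime on other days. Protocol 1.9 reports that a "3.5-fold increase in area under the concentration curve (AUC) was observed in the fed group" after a high-fat meal. Let bedtime doses be *r* times as bioavailable as fasted ones, with *r* = 2 to 3.5 assumed, and let q = 2^(−1/t½). Per unit fasted dose:

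- Day 29 AUCtau = (1 − q)(1 + q^28) + r·q(1 − q^27)
- Steady state under the same pattern = (1 − q) + r·q

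| t½ | r | Day 29 AUCtau | Steady state | Against same pattern | Against fasted CL/F |
|---|---|---|---|---|---|
| 16.8 d | 2 | 1.342 | 1.960 | 1.46 | 0.75 |
| 16.8 d | 3.5 | 2.309 | 3.399 | 1.47 | 0.43 |
| 30 d | 2 | 0.942 | 1.977 | 2.10 | 1.06 |
| 30 d | 3.5 | 1.622 | 3.443 | 2.12 | 0.62 |

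**IR calcifediol.** Protocol Appendix 2, section 5.2, says: "Its half-life is around 18 to 21 days". For the second 28-day interval, 1 − 2^(−56/18) = 0.884 gives 1.13, and 1 − 2^(−56/21) = 0.843 gives 1.19. This row may not appear at all, because SAP 2.2.2 makes monthly AUCtau optional.

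**Paricalcitol, 1 mcg on Days 1–28 and 2 mcg first on Day 29.** Let f = AUC0-24h/AUC0-inf = 1 − 2^(−24/t½) with t½ in hours. Then AUCtau = 2·AUC0-24h + (AUC0-inf − AUC0-24h) = AUC0-inf(1 + f). It follows that LF = 1 + f instead of 1; RA,AUC = 1/f + 1 instead of 1/f, also a factor of 1 + f; and CLss/F is too high by 2/(1 + f). The documents give no paricalcitol half-life, so the values below are assumed.

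| t½ | f | AUCext | LF | RA,AUC (constant dose → raised) | CLss/F factor | LF ÷ 2 |
|---|---|---|---|---|---|---|
| 6 h | 0.938 | 6% | 1.94 | 1.07 → 2.07 | 1.03 | 0.97 |
| 12 h | 0.750 | 25% | 1.75 | 1.33 → 2.33 | 1.14 | 0.88 |
| 18 h | 0.603 | 39.7% | 1.60 | 1.66 → 2.66 | 1.25 | 0.80 |

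The table stops at 18 hours because beyond that AUCext = 2^(−24/t½) passes 40%, where SAP 7.2 already calls AUC0-inf unreliable. The last column shows that dividing by dose over-corrects, since only the last of 29 doses was doubled.

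Equal dose on the two days is not sufficient either. With 1 mcg suspended on Days 22–28 and resumed on Day 29, LF is close to f: 0.94 at 6 hours and 0.60 at 18 hours.

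**CTAP101 halved before Day 29.** With equal bioavailability, the relative fall in BL-adjusted RA,AUC is 0.5(1 − q^m)/(1 − q^29), where *m* is the number of reduced doses.

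- From Day 15 (m = 15): 30.0% at 30 days, 33.1% at 16.8 days.
- From Day 23 (m = 7): 15.3% and 18.0%. With r = 3.5 the 30-day figure is 14.4%.

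These figures do not apply to observed calcifediol, where the endogenous baseline sits in both terms.

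**The case against.** The SAP glosses CLss/F as clearance after multiple administrations and adds a feasibility qualifier, so it never asserts steady state. That is true, but Dose/AUCtau can be computed whenever AUCtau exists, so the qualifier screens nothing out, and the row is still called an apparent clearance with a steady-state subscript.

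The better objection is that the SAP already separates full-dose from adjusted-dose subjects and lists dosing plans and individual parameters. This stands in part: the paricalcitol 1 mcg row is nearly clean, apart from suspensions. The 2 mcg and pooled rows remain uncorrected.

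CTAP101 reductions may also be rare. The documents give no expected number. One subject in 20 with a 30% to 33% fall moves the arm mean by only about 1.5% to 1.7% (30/20 to 33/20).

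A reader might infer several stronger things that the documents do not support:

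- That the CTAP101 value overstates clearance whatever the reference. Against fasted CL/F it may be too low.
- That calcifediol CLss/F should be deleted. SAP CL/F is for paricalcitol only, so this is the only calcifediol clearance planned, and Protocol 2.2.1 lists CL/F as feasible.
- That every RA in the paricalcitol arm is spoiled. Calcifediol there comes from cholecalciferol 800 IU, which is never adjusted.
- That the between-arm model is affected. SAP 7.3 does not name CLss/F, RA or LF, although it leaves room for additional parameters.

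**Conclusion.** The point holds, for descriptive PK tables only. The CTAP101 CLss/F row is not a clearance. It is about 1.43 to 2.05 times too high with equal bioavailability, or 1.46 to 2.12 times against steady state under the same dosing pattern if bedtime doses are 2 to 3.5 times as bioavailable. Against fasted CL/F it is 0.43 to 1.06 times, so no direction should be claimed without naming the reference. IR calcifediol, if reported, is little affected.

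For paricalcitol subjects first given 2 mcg on Day 29, LF and RA,AUC are inflated 1.60- to 1.94-fold and CLss/F 1.03- to 1.25-fold. CTAP101 subjects halved from Day 23 or Day 15 show BL-adjusted RA,AUC lower by about 14–18% or 30–33%.

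All sizes rest on one-compartment linear kinetics. The paricalcitol half-lives and the bedtime bioavailability ratio are assumptions. That CTAP101 is not at steady state on Day 29, and that the ratios lack a dose term, follows from the documents alone.

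**What to change.** 1. Keep the calcifediol parameter but label it: *Dose/AUCtau on Day 29; CTAP101 not at steady state; not interpreted as clearance*.
2. Summarise RA, LF and paricalcitol CLss/F as accumulation, linearity or clearance only for subjects whose dose of the drug producing that analyte was unchanged and not suspended from Day 1 through Day 29. Do not remove subjects from calcifediol RA in the paricalcitol arm because of paricalcitol titration. List the others with a dose-change flag. Do not use dose-normalisation as a substitute.
3. Footnote that the retained set is selected by iPTH, calcium and phosphorus response, since those measures drive both titration and reduction.

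The cost is a few lines of SAP text, one analysis flag, one label and one footnote, with no new data and no change to the noncompartmental method. The drawback is fewer subjects in those rows, from arms of about 20, and a response-selected set.

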3 INVESTIGATIONAL PLAN

3.1 Overall Study Design and Plan

This is a phase 4, multi-center, open-label study to evaluate the comparative safety, efficacy, and PK and **CCI** profiles of CTAP101 Capsules, IR calcifediol, high-dose cholecalciferol, and paricalcitol plus low-dose cholecalciferol to treat SHPT in male and female subjects aged at least 18 years with stage 3 or 4 CKD and VDI. The study will be conducted at multiple sites within the US. Approximately 160 subjects will be screened to enroll approximately 80 eligible subjects who will be randomized 1:1:1:1 (approximately 20 per arm, balanced for body weight) to receive the following medications:

Test Products, Dose, and Mode of Administration:

CTAP101 Capsules (30 mcg/capsule), 60 mcg, by the oral route

[figure not shown]
[figure not shown]
[figure not shown]
[figure not shown]
[figure not shown]
[figure not shown]
Calcifediol immediate-release (IR) (266 mcg/capsule), 266 mcg, by the oral route

Cholecalciferol (50,000 IU/capsule), 300,000 IU, by the oral route

Paricalcitol (1 mcg/capsule) plus cholecalciferol (800 IU/capsule), 1 or 2 mcg plus 800 IU, by the oral route.

If a significant difference in average weight among subjects by treatment group emerges during the course of the study, subjects may be placed into specific treatment groups rather than randomly assigned, in order to try and achieve more balance in the treatment groups by body weight.

The subjects will be housed in a phase 1 unit for approximately 14 to 26 hours at the beginning of the study and on study Day 29 to provide the blood samples required for a detailed determination of the PK profiles for serum calcifediol and **CCI**

Blood samples for some of the PK/**CCI** assessments will be collected in the phase 1 unit at -2, 0, 2, 4, 6, and 12 hours either in the phase 1 unit or during outpatient visit, at 24 hours; during outpatient visit for 48 hours; and then weekly following the first dose and the Day 29 dose of each medication. Blood samples for other **CCI** assessments will be collected at less frequent intervals. Urine collections (24-hour) will be obtained at pre-treatment baseline (Visits 2 and 3), starting immediately after dosing on Day 1 (Visit 4) and Day 29 (Visit 10) and at the end of study (Visit 16) or early termination (ET). The schedule for blood and urine sample collections is delineated in [Section 7](#) (Study Activities) and in [APPENDIX 1](#).

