5.2 Pharmacokinetic properties

Vitamin D

Sun exposure: UVB light converts 7-dehydrocholesterol, found in the skin, to colecalciferol.

Absorption: Vitamin D is easily absorbed in the small intestine. Food intake potentially increases the absorption of vitamin D.

Distribution and biotransformation: Colecalciferol and its metabolites circulate in the blood bound to a specific globulin. Colecalciferol is converted in the liver by hydroxylation to 25-hydroxycholecalciferol. It is then further converted in the kidneys to 1,25-dihydroxycholecalciferol. 1,25-dihydroxycholecalciferol is the active metabolite responsible for increasing calcium absorption. Vitamin D, which is not metabolised, is stored in adipose and muscle tissues.

After a single oral dose of colecalciferol, the maximum serum concentrations of the primary storage form are reached after approximately 7 days. 25(OH)D₃ is then slowly eliminated with an apparent half-life in serum of about 50 days. Colecalciferol and its metabolites are excreted mainly in the bile and faeces.

Elimination: Vitamin D is excreted mainly in bile and faeces with a small percentage found in urine.

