#### Pharmacokinetic Parameters Following the First Dose (Day 1):

*Note: The following parameters will be calculated using the data through 24 hours (once daily dosing regimens) or 28 days (monthly dosing regimens) after the first dose on Day 1 for each of the analytes, as indicated.*

$C_{\max}$ :	Maximum concentration, observed by inspection of individual study participant concentration-time profiles.
$C_{\max,0-24h}$ :	Maximum concentration over a 24-hour interval, observed by inspection of individual study participant concentration-time profiles. Presented for the monthly dosing regimens only. (For the daily dosing regimens, $C_{\max}$ will be equivalent to $C_{\max,0-24h}$ .)

$T_{\max}$ :	Time of maximum concentration, obtained directly from the observed concentration-time data.
$T_{\max,0-24h}$ :	Time of maximum concentration over a 24-hour interval, obtained directly from the observed concentration-time data. Presented for the monthly dosing regimens only. (For the daily dosing regimens, $T_{\max}$ will be equivalent to $T_{\max,0-24h}$ .)
$AUC_{0-t}$ :	AUC from time 0 to the last measurable time point, calculated by linear-log trapezoidal summation.
$AUC_{0-t'}$ :	AUC from time 0 to a fixed time point $t'$ , calculated by linear-log trapezoidal summation. This will include the AUC from time 0 to 24 hours ( $AUC_{0-24h}$ ) for all dosing regimens and AUC from time 0 to 28 days ( $AUC_{0-28d}$ ) for the monthly dosing regimens only.
$AUC_{0-\infty}$ :	AUC from time 0 extrapolated to infinity, calculated as $AUC_{0-t} + C_{\text{last}}/\lambda_z$ , where $C_{\text{last}}$ is the last measurable concentration (paricalcitol only).  The reliability of $AUC_{0-\infty}$ values is contingent upon the percentage obtained by extrapolation ( $AUC_{\text{ext}}$ ), where $AUC_{\text{ext}}$ is $>40\%$ , $AUC_{0-\infty}$ values are considered unreliable.
$AUC_{\text{ext}}$ :	Percentage of $AUC_{0-\infty}$ obtained by extrapolation, calculated as $[(AUC_{0-\infty} - AUC_{0-t})/AUC_{0-\infty}] \times 100$ ; (a diagnostic parameter calculated and listed in the data listing, but not included in the descriptive statistics; paricalcitol only).

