### 7.3 Statistical Analysis of Pharmacokinetic Parameters

As an exploratory analysis, PK parameters for observed and BL-adjusted serum calcifediol will be compared between treatments using a mixed-effects model for the PK population. The dependent variable will be the value of the PK parameter. The model will include a term for treatment and BL calcifediol as a covariate. The PK parameters

compared may include  $C_{max}$  and  $AUC_{0-24h}$  for Day 1 and  $C_{max}$ ,  $AUC_{0-24h}$  (ie,  $AUC_{tau}$  for daily dosing regimen), and  $C_{avg}$  for Day 29. Additional parameters (eg, alternative  $AUC_{0-t}$  parameters) may be compared (and/or substituted) as deemed appropriate.

[figure not shown]
Treatment least-squares means and least-squares differences and 95% confidence intervals for the difference will be constructed for the values of each parameter. In addition, the  $P$  values will be presented for treatment and BL in the analysis table.

The SAS Proc Mixed code is as follows:

[figure not shown]
```
PROC MIXED DATA = adpc;
  BY paramn paramcd param;
  CLASS trtp;
  MODEL aval = trtp base_calcifediol;
  ESTIMATE 'CTAP101 Capsules vs. Calcifediol IR' trtp 1 -1 0 0 / cl;
  ESTIMATE 'CTAP101 Capsules vs. Cholecalciferol' trtp 1 0 -1 0 / cl;
  ESTIMATE 'CTAP101 Capsules vs. Paracalcitol plus cholecalciferol' trtp 1 0 0 -1 / cl;
  RUN;
```

[figure not shown]
Alternative statistical analyses may be provided if insufficient data or issues with the model are found.

CCI

CCI

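### Whole-study calcifediol exposure is planned for the monthly arms only, so the only AUC named for comparing regimens is a dosing-day AUC0-24h, whose Day 1 contrast with IR calcifediol can point the opposite way from 56-day exposure

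*SAP*

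**What the plan says.** Two arms are dosed daily (CTAP101; paricalcitol plus low-dose cholecalciferol) and two on Days 1 and 29 (IR calcifediol; high-dose cholecalciferol).

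- **Day 1 parameters** (SAP 7.2): "The following parameters will be calculated using the data through 24 hours (once daily dosing regimens) or 28 days (monthly dosing regimens").
- **Day 29 parameters** (SAP 7.2): "The following parameters will be calculated using the data through 24 hours for the once daily dosing regimens"; the monthly regimens use data to Day 57.
- **Whole study** (end of SAP 7.2): "measures of exposure over the entire 56-day study period will be determined for calcifediol (for the monthly dosing regimens only"). AUC0-56d is built as the Day 1 AUC0-28d plus the Day 29 AUCtau.
- **Endpoint list** (SAP 2.2.2): item 4 keeps AUC0-28d for the monthly regimens. Item 5 lists AUC0-56d with no arm restriction. Item 6 makes AUCtau conditional in the monthly regimens. Item 9 attaches Cavg,56d to the monthly regimens.
- **Between-arm model** (SAP 7.3): "PK parameters for observed and BL-adjusted serum calcifediol will be compared between treatments using a mixed-effects model for the PK population". The parameters "compared may include $C_{max}$ and $AUC_{0-24h}$ for Day 1", and Cmax, AUC0-24h and Cavg for Day 29. CTAP101 is contrasted with each other arm. Further parameters "may be compared (and/or substituted) as deemed appropriate".
- **Sampling** (Protocol 3.1): beyond 48 hours, samples are taken "then weekly following the first dose and the Day 29 dose of each medication". SAP 3.3 likewise does not limit this by arm.

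**The concern.** The objective is repeated-dose pharmacokinetics over eight weeks, but the AUC that every arm shares covers a single dosing day. That day means something different in each regimen.

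- For IR calcifediol, which peaks at about 4 hours (Protocol Appendix 2, section 5.2), it is the highest day of a 28-day interval.
- After cholecalciferol, "the maximum serum concentrations of the primary storage form are reached after approximately 7 days" (Protocol Appendix 4, section 5.2), so the window closes about six days too early.
- For CTAP101, Day 1 is one dose of 56. Day 29 is a point on a rising curve: Protocol 3.2 says steady state was not reached at 6 weeks.

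SAP 7.3 attaches confidence intervals and P values to these contrasts. A reader could take the Day 1 AUC result as showing which regimen delivers more calcifediol, when it mainly shows what happened on the sampled day.

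**Working it through.** The documents give no exposure ratio to reproduce. The check compares CTAP101 with IR calcifediol over each window.

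**Inputs from the documents**
- Doses (Protocol 5.2): CTAP101 60 mcg daily; IR calcifediol 266 mcg on Days 1 and 29.
- Bioavailability: CTAP101 about 25% fasted (Protocol 1.9); IR calcifediol 75–80% absorbed, midpoint 77.5% (Appendix 2, section 5.2).
- Half-life: about 30 days on repeated CTAP101 (Protocol 3.2); 18–21 days for the IR product, midpoint 19.5 (Appendix 2, section 5.2).
- Level: mean total 25-hydroxyvitamin D of 67 ng/mL on 60 mcg daily in the six-week phase 2b study (Protocol 3.2).

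**Assumed:** baseline 20 ng/mL (range 15–25), linear one-compartment kinetics, equal distribution volumes, immediate absorption, every dose taken and none changed, bedtime 14 hours after the morning dose time.

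**Step 1, dose arithmetic**
- Day 1: 60/266 = 0.23. Absorbed: 60 × 0.25 = 15 mcg against 266 × 0.75 to 0.80 = 200–213 mcg.
- 56 days: 3,360/532 = 6.3. Absorbed: 840 mcg against 399–426 mcg.

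The direction already differs between the two windows.

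**Step 2, rise per dose**
With k = ln 2/30:
- CTAP101: (67 − 20)/[(1 − e^(−42k))/(1 − e^(−k))] = 47/27.2 = 1.73 ng/mL.
- IR calcifediol: 1.73 × (266 × 0.775)/(60 × 0.25) = 23.8 ng/mL.

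**Step 3, AUC by superposition**
A dose giving rise d at time s contributes d(1 − e^(−k(T−s)))/k up to time T, using each product's own k. With half-lives of 30 and 19.5 days, baseline-adjusted, in ng·day/mL:
- Day 1, 0–24 h: 1.7/23.3 = 0.07
- Day 29, 0–24 h: 37.0/32.0 = 1.16
- 0–56 days: 1,836/998 = 1.84
- Day 29 Cavg with tau = 28 days for IR: 37.0/(577/28) = 37.0/20.6 = 1.80

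| CTAP101/IR ratio | Half-lives 30 and 19.5 d | 30 and 30 d | 20 and 20 d |
|---|---|---|---|
| Day 1 AUC0-24h, adjusted | 0.07 | 0.07 | 0.07 |
| Day 29 AUC0-24h, adjusted | 1.16 | 1.03 | 1.00 |
| Day 29 Cavg, IR over 28 days, adjusted | 1.80 | 1.39 | 1.54 |
| 0–56 days, adjusted | 1.84 | 1.49 | 1.54 |
| Day 1 AUC0-24h, observed | 0.50 | 0.50 | 0.46 |
| 0–56 days, observed | 1.40 | 1.25 | 1.28 |

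The baseline and the 67 ng/mL cancel from the adjusted ratios; they affect only the observed ones. If Cavg in the IR arm is taken over 24 hours, its ratio is the Day 29 AUC0-24h row.

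**Sensitivity**
- First-order absorption (10/day for CTAP101, 30/day for IR), bioavailability 0.25 against 0.75–0.80, half-lives 18–30 days: Day 1 0.066–0.071, Day 29 AUC0-24h 0.98–1.25, 56 days 1.44–1.99.
- IR bioavailability set to 1.0: Day 1 0.05, Day 29 AUC0-24h 0.78–0.94, 56 days 1.15–1.49.
- The reversal occurs whenever CTAP101/IR relative bioavailability lies above about 0.17–0.22 and below about 4.7. The documents give 0.25/0.80 = 0.31 to 0.25/0.75 = 0.33.

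**Other arm.** With a 7-day peak and a 50-day half-life (Appendix 4, section 5.2), the mean calcifediol rise in the first 24 hours after cholecalciferol is about 0.29 of its 28-day mean. No CTAP101/cholecalciferol ratio was derived.

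**The case against.** The strongest reply is that AUC0-24h is not the whole comparison. SAP 7.3 also names Day 29 Cavg. SAP 7.2 defines this as AUCtau/tau, and tau is 28 days in the monthly arms. On that definition the model gives 1.39–1.80 against a whole-study 1.49–1.84: the right direction and nearly the right size. Monthly-arm Cmax also spans 28 days, so the cholecalciferol peak is captured there. This stands, so it would be wrong to infer that every planned comparison is confined to 24 hours. It does not remove the point. SAP 7.2 also permits a 24-hour Cavg in the monthly arms, SAP 2.2.2 makes their AUCtau conditional, and a 28-day Cmax set against a 24-hour Cmax is a comparison over unequal windows.

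A reader might also infer that no longer AUC could ever be compared. The documents do not say that. SAP 2.2.2 item 5 is unrestricted, its opening sentence allows additional parameters, and SAP 7.3 allows additions and substitutions. What is missing is a defined 28-day or 56-day parameter for the daily arms and a settled choice among the options.

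Further, SAP 7.1 summarises and plots calcifediol by visit and treatment, so the CTAP101 time course will be visible, though without an estimated contrast or interval. The study is descriptive and the model exploratory, which limits the stakes. Redacted SAP text may hold other summaries and cannot be checked.

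**Conclusion.** The point holds as a gap in the exposure comparison and an inconsistency between SAP 2.2.2 and 7.2. The named AUC contrast of CTAP101 with IR calcifediol would be about 0.07 on Day 1, opposite in direction to 56-day exposure of about 1.5–1.8. On Day 29 it would be about 1.0–1.2, which understates that exposure. Observed values move all ratios towards 1 but keep the Day 1 reversal.

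These sizes rest on linear kinetics, equal volumes, full dosing and bioavailability figures from separate sources. The direction on Day 1 is robust; the 56-day excess is less so, falling to 1.15 if IR bioavailability is 1.0.

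It is tempting to extend the reversal to all three CTAP101 contrasts, but it has been derived for IR calcifediol only. Nor do the documents support saying that the study's conclusions would be wrong, since no decision is tied to AUC0-24h. This is a cheap and worthwhile improvement.

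**What to change.** 1. In SAP 7.2, derive AUC0-28d, AUC28-56d, AUC0-56d and Cavg,56d for calcifediol in all four arms, from the weekly samples plus those around Days 1 and 29.
2. Define AUC0-56d as AUC0-28d + AUC28-56d. Deleting the monthly-only restriction is not enough: AUCtau is 24 hours in the daily arms, so the present formula would give CTAP101 28 days plus one day. In the model that is 550 + 37 = 587 of 1,836 ng·day/mL, about 32%.
3. Amend the data-window notes above the Day 1 and Day 29 parameter lists, and SAP 2.2.2 items 4 and 9, to match; item 5 then agrees with 7.2.
4. In SAP 7.3, name AUC0-56d or Cavg,56d as an exposure contrast, fix one Cavg window for the monthly arms, and label AUC0-24h as a dosing-day measure.

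**Cost:** SAP wording and a few more derived parameters. The daily arms would rely on the weekly samples described in Protocol 3.1 and SAP 3.3. The visit-level lists in Protocol 7.2.3 and 7.2.6 are partly redacted, so the sponsor should confirm that calcifediol is assayed at those visits in every arm. Weekly samples would fall at varying times after the last daily dose. With half-lives of weeks this matters little: a linear trapezoid on the planned times recovered the modelled CTAP101 0–56 day AUC to within 1%.
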